14.2.1.2 Interaction

Under no interaction, the risk of a DLT at dose d_1 of VAY736 and dose d_2 of Ibrutinib is:

$$\pi_{12}^0(d_1, d_2) = 1 - (1 - \pi_1(d_1))(1 - \pi_2(d_2))$$

To allow for interaction between VAY736 and dose d_2 of Ibrutinib, an odds multiplier is introduced. The risk of DLT for combination dose (d_1, d_2) is then given by:

$$\text{odds}(\pi_{12}(d_1, d_2)) = \exp(\eta \times d_1/d_1^* \times d_2/d_2^*) \times \text{odds}(\pi_{12}^0(d_1, d_2))$$

where $\text{odds}(\pi) = \pi/(1 - \pi)$; and η is the log-odds ratio between the interaction and no interaction model at the reference doses. i.e., 3.0 mg/kg ($1.5\text{mg/kg} * 2$) of total cycle 1 VAY736 and 420 mg of daily Ibrutinib. Here $\eta = 0$ corresponds to no interaction, with $\eta > 0$ and $\eta < 0$ representing synergistic and antagonistic toxicity respectively.

14.2.2 Prior specifications

The Bayesian approach requires the specification of prior distributions for all model parameters, which include the single agent parameters $\log(\alpha_1)$, $\log(\beta_1)$ for VAY736, $\log(\alpha_2)$, $\log(\beta_2)$ for Ibrutinib, and the interaction parameter η . A meta-analytic-predictive (MAP) approach was used to derive the prior distribution for the single-agent model parameters for VAY736. A weakly-informative prior is derived for the single-agent model parameters for ibrutinib.

14.2.2.1 Prior distribution for the logistic parameters

14.2.2.1.1 Description of the meta-analytic-predictive (MAP) approach

The aim of the MAP approach is to derive a prior distribution for the logistic parameters $(\log(\alpha^*), \log(\beta^*))$ of the new trial using DLT data from historical studies.

Let r_{ds} and n_{ds} be the number of patients with a DLT, and the total number of patients at dose d in historical study VAY736Y2101 and each of the four autoimmunity clinical program historical studies, i.e., $s=1,2,3,4,5$ represent data from VAY736Y2101, and autoimmunity historical studies VAY736X2101, VAY736X2201, VAY736X2202, and VAY736X2203, respectively. The corresponding probability of a DLT is π_{ds} . The model specifications are as follows:

$$\begin{aligned} r_{ds} \mid \pi_{ds} &\sim \text{Bin}(\pi_{ds}, n_{ds}) \\ \text{logit}(\pi_{ds}) &= \log(\alpha_s) + \beta_s \log(d/d^*) \\ (\log(\alpha_s), \log(\beta_s)) \mid \mu, \psi_{g(s)} &\sim \text{BVN}(\mu, \psi_{g(s)}), \quad s = 1, \dots, 5 \\ (\log(\alpha^*), \log(\beta^*)) \mid \mu, \psi_1 &\sim \text{BVN}(\mu, \psi_1) \end{aligned}$$

The parameter $\mu = (\mu_1, \mu_2)$ is the mean for the logistic parameters, and ψ_g is the between-trial covariance matrix for exchangeability group $g = 1, 2$. Covariance matrix ψ_g is defined by the standard deviations τ_{g1} , τ_{g2} , and correlation ρ (a common value for ρ is used across all groups). The parameters τ_{g1} and τ_{g2} quantify the degree of between trial heterogeneity for exchangeability group g . With different prior distributions for the parameter sets (τ_{g1}, τ_{g2}) it is possible to allow for differential discounting for the historical strata. In this way the quality and relevance of historical data can be accounted for in the meta-analysis. The following priors will be used for these parameters:

- normal priors for μ_1 and μ_2 ,
- log-normal priors for τ_{g1} and τ_{g2} , and
- a uniform prior for ρ .

The MAP prior for single-agent model parameters in the new trial, $(\log(\alpha^*), \log(\beta^*))$, is the predictive distribution

$$(\log(\alpha^*), \log(\beta^*)) \mid (r_{ds}, n_{ds} : s = 1, \dots, 5)$$

Since the predictive distribution is not available analytically, MCMC is used to simulate values from this distribution. This is implemented using JAGS version 4-6. The sample from this distribution is then approximated by a mixture of bivariate normal (BVN) distributions. BVN mixtures with increasing numbers of mixture components are fitted to the sample using the expectation-maximization (EM) algorithm (Dempster 1977). The optimal number of components of the mixture is then identified using the Akaike information criterion (AIC) (Akaike 1974).

14.2.2.1.2 Single agent VAY736

For the MAP model for VAY736, total cycle 1 reference dose $d^* = 3.0 \text{ mg/kg}$ is used; data from $S = 5$ historical studies is available; and $G = 2$ exchangeability groups are assumed.

Weakly informative priors are assumed for μ_1 and μ_2 , with means corresponding to a risk of DLT at the reference dose of 9.3% (i.e., based on the assumed 3.6% DLT at the starting dose from the model (1) above) , and a tripling in dose leading to a doubling in the odds of the risk of a DLT. For the 2 exchangeability groups the priors for (τ_{g1}, τ_{g2}) are assigned such that (1) their medians correspond to small and moderate between trial heterogeneity, and (2) their uncertainty (95% prior interval) cover plausible between-trial standard deviations (Neuenschwander 2014). The prior distributions for the model used for deriving the MAP priors are specified in Table 14-3.

Table 14-3 Prior distributions for the parameters of the MAP model used to derive the prior for single-agent VAY736 model parameters

Exchangeable group	Parameter	Prior distribution
	μ_1	$N(\text{mean} = \text{logit}(0.093), \text{sd} = 2)$
	μ_2	$N(\text{mean} = \log(\log(2)/\log(3)), \text{sd} = 1)$
	ρ	uniform(-1,1)
1 small heterogeneity	τ_{11}	lognormal($\text{mean} = 0.125, \text{sd} = \log(2)/1.96$)
	τ_{12}	lognormal($\text{mean} = 0.0625, \text{sd} = \log(2)/1.96$)
2 moderate heterogeneity	τ_{21}	lognormal($\text{mean} = 0.25, \text{sd} = \log(4)/1.96$)
	τ_{22}	lognormal($\text{mean} = 0.125, \text{sd} = \log(4)/1.96$)

Historical data

Autoimmunity clinical studies VAY736X2101, VAY736X2201, VAY736X2202, VAY736X2203 (Assigned to exchangeability group 2) and study VAY736Y2101 (Assigned to exchangeability group 1) subject exposures to VAY736 and DLTs are presented in the Table 14-4 below.

A review of AE records of the patients in autoimmunity clinical studies did not indicate any significant toxicity in the historical studies presented in Table 14-4 below. VAY736 was well tolerated, only few SAEs were observed and none of the SAEs were drug related. In addition those few SAEs that occurred in autoimmunity studies are irrelevant to current CLL patients.

For VAY736Y2101 there was one patient reported as dose limiting toxicity and SAE (grade 3 hemolytic autoimmune anemia), however this patient had baseline autoimmune anemia.

Substantial heterogeneity is assumed due to the difference in population, indication and dosing schedule from autoimmune studies to current study; Small heterogeneity is expected between VAY736Y2101 and current study. Therefore two exchangeability groups are assigned as below. The new trial is assigned to exchangeability group 1.

Table 14-4 Historical DLT data from Studies VAY736X2101, VAY736X2201, VAY736X2202, VAY736X2203 and VAY736Y2101

Historical studies/ Exchangeability groups (G)	Total cycle 1 dose (<mg/Kg>)	#of DLTs/# of evaluable pts
VAY736X2101/2	.0003	0/3
	.001	0/3
	.003	0/3
	.01	0/4
	.03	0/3
	.1	0/3
	.3	0/9
	.86	0/12
	1	0/9
	3	0/3
VAY736X2201/2	10	0/3
	3	0/6
VAY736X2202/2	10	0/17
	10	0/8
VAY736X2203/2	3	0/7
	10	0/5
VAY736Y2101/1	.008	1/3

Notes:

1. The data is based on Investigators Brochure released on 29-Aug-2016 and safety cut-off date on 30-Jun-2016.
2. The total cycle 1 dose (mg/kg) for VAY736 treatment is used to incorporate data from different administrations.
3. DLT presented in the VAY736Y2101 is within cycle 1 (28 days window); DLT presented in the autoimmune studies are within study duration which may occur beyond cycle 1, which can be deemed as conservative estimate for counting AEs to occur within the first cycle of VAY736 treatment.

To make the prior more robust, an additional mixture component corresponding to a high toxicity scenario is added to the MAP prior. For this component, the median probability of DLT at the total cycle 1 reference dose 3.0 mg/kg is 12%; the median for the prior distribution of $\log(\beta)$ is set to $\log(\log(2)/\log(3))$ at the reference dose which assumes a tripling dose leads to a doubling of the odds of DLT. The median DLT rates of total cycle 1 doses 0.6 mg/kg, and 4.0 mg/kg are approximately 3.3%, and 15.4%, respectively. Standard deviations for $\log(\alpha)$ and $\log(\beta)$ are set to 2 and 1 respectively, with correlation $\rho = 0$.

The weight assigned to the 3 components of the MAP prior is 0.80 in total, and the weight assigned to the high toxicity prior component is 0.20. The mixture components are weighted based upon *a priori* assessment of their relevance to the toxicity of combination of VAY736 and Ibrutinib in humans. The prior distribution is described in full in [Table 14-3](#).

14.2.2.1.3 Single agent Ibrutinib

Based on clinical toxicology data (Section 1.2.4.1) a weakly informative prior is derived for which the median probability of DLT at dose 420 mg daily is assumed to be 8%. The review of historical safety data were summarized in the [Table 14-5](#) below. The observed historical rate of discontinued from study due to adverse events is approximately 4% at 420 mg ibrutinib daily. Due to the lack of precise DLT data from historical studies, the current 8% DLT for cycle 1 is assumed to be conservative.

The median for the prior distribution of $\log(\beta)$ was set to 0, to correspond to a doubling of dose leading to a doubling of the odds of DLT. The standard deviation for $\log(\alpha)$ is derived assuming that there is 90% probability that the DLT rate is lower than 33% at 420 mg daily reference dose. The standard deviation for $\log(\beta)$ is 1. The correlation between the $\log(\alpha)$ and $\log(\beta)$ is $\rho = 0$. The prior distribution is described in full in [Table 14-6](#).

Table 14-5 Historical data for ibrutinib

Study #	Dose of ibrutinib (daily)	# of discon. due to AEs / # of evaluable patients (%)
(Byrd et al 2013)	420mg	2/51(4%)
	840mg	4/33(12%)
(Byrd JC et al 2015)	420mg	8/195(4%)

14.2.2.2 Prior distribution for the interaction parameters

Although no interaction is expected for the two agents, uncertainty remains. Therefore, a normal prior for the log-odds multiplier η centered at 0 is used that allows for both synergistic and antagonistic toxicity.

- η is normally distributed, with mean 0, and standard deviation 0.858
- At the total cycle 1 starting dose of 0.6 mg/kg (0.3 mg/kg *2) the corresponding distribution for the odds ratio has mean 1.000 and a 97.5th percentile of 1.4, i.e. 1.4-fold increase in odds of DLT due to interaction compared to no interaction.

14.2.2.3 Summary of prior distributions

The prior distributions of the model parameters are summarized in [Table 14-6](#). Prior summaries for DLT rates for are summarized in [Table 14-7](#).

Table 14-6 Prior distribution for the model parameters

Parameter	Mean	Standard Deviations (SD)	Correlation	Weight
Single agent VAY736 MAP prior, total cycle 1 reference dose 3.0 mg/kg				
BVN mixture ($\log(\alpha_1), \log(\beta_1)$)				
Three-component MAP prior	Component 1 (-4.795, -1.876)	(0.908, 0.665)	-0.137	0.355
	Component 2 (-4.035, -1.443)	(0.645, 0.490)	-0.017	0.347
	Component 3 (-3.770, -2.310)	(0.540, 0.668)	0.299	0.098
High-tox component	Component 4 (-1.992, -0.461)	(2, 1)	0	0.200
Single agent Ibrutinib weakly-informative prior, reference dose 420 mg				
BVN ($\log(\alpha_2), \log(\beta_2)$)				
	(-2.442, 0)	(1.353, 1)	0	N/A
Interaction parameter η				
Normal				
η	0	0.858	N/A	N/A

Table 14-7 Summary of prior distribution of DLT rates

VAY736 dose (mg/kg) Q2W	Prior probabilities that P(DLT) is in the interval:			Mean	SD	Quantiles		
	[0, 0.16)	[0.16, 0.33)	[0.33, 1]			2.5%	50%	97.5%
In combination with Ibrutinib 420mg daily								
0.1	0.665	0.206	0.129	0.156	0.156	0.013	0.101	0.600
0.3	0.650	0.212	0.139	0.164	0.163	0.014	0.106	0.628
1.0	0.606	0.218	0.176	0.186	0.188	0.013	0.117	0.725
2.0 (intermediate)	0.561	0.195	0.245	0.223	0.236	0.007	0.129	0.861
3.0	0.534	0.163	0.303	0.260	0.282	0.003	0.137	0.945

- The grey shaded rows indicate dose combinations not meeting the EWOC criterion, that there is $\geq 25\%$ chance of excessive toxicity, i.e. DLT rate in [0.33, 1].

- The starting dose level is highlighted in bold. Total cycle 1 VAY736 dose is used in the BLRM. i.e., 2 * mg/Kg Q2W.

Change in dose schedule

In the case that additional dosing schedules for VAY736 are explored during dose-escalation, a BLRM of the same functional form will be used to estimate the dose-DLT relationship for each new schedule. Data from previous, or concurrently explored schedules will be used to inform the dose escalation for the new schedule. At each time the decision is taken to explore a new schedule, the model to be used to guide escalation in that schedule will be constructed. The model will be finalized prior to first patient treated under the new schedule, and will be documented in full in CSR Section 16.1.9.

14.2.3 Hypothetical on-study data scenarios

To illustrate the performance of the Bayesian model used to guide dose escalation, hypothetical dose escalations scenarios following the provisional dose levels specified in [Table 14-8](#) are displayed. In each case, the maximum dose that can be used in the next cohort of patients is shown. This maximum dose is determined using the model based assessment of the risk of DLT in future patients and the dose escalation rules as described in [Section 6.2.3](#). In practice a dose below the maximum might be chosen based on additional safety, PK or PD information ([Section 6.2.1.1](#)).

Table 14-8 Hypothetical dose escalation scenarios

Scenario	Dose	Number of		Next dose combination		
	Ibrutinib 420 mg daily + VAY736 (mg/kg) Q2W	Patients	DLTs	Ibrutinib 420 mg daily + VAY736 (mg/kg) Q2W	Median P(DLT)	P(excessive toxicity)
1	0.3	3	0	1.0	0.076	0.065
2	0.3	3	1	0.3	0.173	0.192
3	0.3	3	2	stop		
4	0.3	4	1	1.0	0.163	0.191
	0.3	3	0	3.0	0.052	0.111
5	1.0	4	0			
	0.3	3	0	1.0	0.124	0.072
6	1.0	4	1			
	0.3	3	0	3.0	0.131	0.233
7	1.0	6	1			
	0.3	3	0	1.0	0.185	0.147
8	1.0	6	2			
	0.3	4	0	1.0	0.105	0.044
9	1.0	5	1			
	0.3	4	0	3.0	0.122	0.218
10	1.0	6	1			
	0.3	4	1	3.0	0.082	0.145
11	1.0	5	0			

14.2.4 Operating characteristics

A simulation study is used to illustrate the long run performance of the Bayesian dose escalation model. Several example scenarios were investigated ([Section 14.2.4.1](#)), and in each case 1000 trials were simulated, with results summarized in [Section 14.2.4.1.1](#).

14.2.4.1 Scenarios

Table 14-9 shows three dose-DLT scenarios as follow:

- Scenario 1 represents the situation in which the true probability of DLT is in line with the prior, i.e. $P(DLT) = \text{prior median}$.
- Scenario 2: the odds of DLTs are 1.5-fold larger than the ones of scenario 1.
- Scenario 3: the odds of DLTs increases steeper and rapidly early as dose goes higher, where the DLT rate at 1.0 mg/kg bi-weekly is approximately 55%.

Table 14-9 True probability of DLT for simulation scenarios

Test scenarios	Dose of VAY736(bi-weekly) in combination with Ibrutinib 420 (mg daily)				Note
	0.1 mg/kg	0.3 mg/kg	1.0 mg/kg	3.0 mg/kg	
1	0.101	0.106	0.117	0.137	True dose-DLT relationship based on prior median rates
2	0.152	0.159	0.176	0.206	1.5-fold odds increased from scenario 1
3	0.101	0.180	0.550	0.700	More toxic and steeper than scenario 1

14.2.4.1.1 Simulation details

Data for 1000 trials are simulated for each scenario and the total minimum number of DLT to control the declaration of MTD is fixed to one. The starting dose combination is set to 420 mg daily Ibrutinib and 0.3mg/kg Q2W VAY736 and follows the protocol specifications (Section 6.2.3). At each dose escalation, the highest VAY736 dose in combination with ibrutinib 420 mg daily satisfying the EWOC criterion is chosen for the next cohort.

The number of patients to enroll in each cohort and stopping rules used to declare MTD are defined as:

- Cohort size: 3-6
- Minimum number of patients enrolled: 15
- Maximum number of patients enrolled: 40
- Minimum number of patients enrolled at a given dose combination in order to declare MTD: 6

Simulation results

Operating characteristics were reviewed for the simulations to compare the relative performance under each true scenario. The metrics reviewed were:

- Metric I: Average proportion of patients in target dose region ($\geq 16\% - 33\%$).
- Metric II: Average proportion of patients in over dose region ($\geq 33\%$).
- Metric III: Average proportion of patients in under dose region ($< 16\%$).
- Metric IV: Proportion of trials with MTD in target dose region ($\geq 16\% - 33\%$).

- Metric VI: Proportion of trials with MTD in under dose region (< 16%).
- Stopped: Proportion of trials stopped with no MTD identified.
- Ave N: Average number of patients dosed.
- Ave DLT: Average number of DLTs observed.

Table 14-10 Summary of simulation results

Scenario	Metrics (%)							Ave N	Ave DLT
	I	II	III	IV (Target MTD)	V (Overdose MTD)	VI (Under- dose MTD)	Stopped		
1	0	0	100	0	0	91.4	8.6	18.8	2.3
2	62.2	0	37.8	66.3	0	15.6	18.1	17.3	3.0
3	54.8	39.0	6.2	39.9	7.7	0.2	52.2	14.4	4.7

The operating characteristics show that the BLRM with the derived informative prior perform reasonable under the three hypothetical scenarios investigated. In scenario 1 all patients are treated in under dose region due to the low assumed true DLT rate in all dose levels (less than 13%). The proportion of patients treated in the target dose region is about 62% (Metric I) in scenario 2.

The probabilities to identify a MTD in the target dose region (Metric IV) are approximately 66% for scenario 2 and 40% for scenario 3, respectively. The chance of identifying a MTD that is in fact excessively toxic is controlled at 8% for scenario 3.

Approximately 9-19% of the trials stopped in Scenario 1 and 2. Even the lowest dose has a considerable DLT rate of above 10-15% at the starting dose even though the whole dose curve are both relatively flat. In the scenario 3, the chance of stopping without identifying a MTD is 52% due to the relative high toxicity at the starting dose, resulting in a high probability of seeing DLTs early in the dose escalation.

The average number of patients needed are between 14 to 19, and approximately 2-5 DLT's are expected.

References

Akaike H. (1974) A new look at the statistical model identification. *IEEE Transactions on Automatic Control*, AC-19, 716–723

14.3 Appendix 3 – Drugs which are prohibited or to be used with caution

In general, the use of any concomitant medication deemed necessary for the care of the patient is permitted in this study, except as specifically prohibited below. Combination administration of study drugs could result in drug-drug interactions (DDI) that could potentially lead to reduced activity or enhanced toxicity of the concomitant medication and/or ibrutinib.

The following lists are based on the Novartis PK Sciences DDI List (v01 released in January 2018). The FDA's Guidance for Industry Drug Interaction Studies – Study Design, Data Analysis and Implications for Dosing and Labeling (2017) is the basis of the Novartis PK Sciences DDI List, and it was supplemented with Indiana University (IU) Flockhart Table™ and University of Washington (UW) Drug Interaction Database.

The list of medications in [Table 14-11](#) is meant to provide guidance only and it is not a comprehensive list. If a patient is required to take a medication that is not in the list, but there may be a risk of DDI, please contact the Novartis clinical study team for further advice.

Please contact the Novartis Medical monitor with any questions.

Table 14-11 Drugs prohibited while on study

Category	Drug Names
Strong inhibitors of CYP3A	VIEKIRA PAK ¹ , indinavir/ritonavir ¹ , tipranavir/ritonavir ¹ , ritonavir, cobicistat ,indinavir, ketoconazole, troleandomycin, telaprevir, danoprevir/ritonavir ¹ , elvitegravir/ritonavir ¹ , saquinavir/ritonavir ¹ , lopinavir/ritonavir ¹ , itraconazole, voriconazole, mibefradil, , clarithromycin, posaconazole, telithromycin, grapefruit juice ² , conivaptan, nefazodone, neflifinavir, , idelalisib, boceprevir, atazanavir/ritonavir ¹ , darunavir/ritonavir ¹
Moderate inhibitors of CYP3A4/5	aprepitant, amprenavir, atazanavir, cimetidine, ciprofloxacin, crizotinib, cyclosporine, darunavir, diltiazem, dronedarone, erythromycin, faldaprevir, fluconazole, grapefruit juice ² , imatinib, isavuconazole, netupitant, nilotinib, tofisopam, Schisandra sphenanthera (nan wu wei zi) ³ , asafoetida resin (Ferula asafoetida) ³ , verapamil Seville oranges or products containing Seville oranges (e.g. Marmalades) ² .
Strong inducers of CYP3A4/5	carbamazepine, enzalutamide, lumacaftor, phenobarbital, phenytoin, rifabutin, rifampin, mitotane, St. John's wort (Hypericum perforatum) ³
Combination therapy. (in some cases combinations with ritonavir have been listed as moderate inhibitors of CYP3A in the UW database, the have all been listed as strong in the DDI guide to avoid any potential confusion)	FDA Draft Guidance for Industry, Drug Interaction Studies – Study Design, Data Analysis, and Implications for Dosing and Labeling (2017) (/fdagov/downloads/drugs/guidancecomplianceregulatoryinformation/guidances/ucm292362.pdf), Indiana University (IU) Flockhart Table™ (/drug-interactions.medicine.iu.edu/), University of Washington (UW) Drug Interaction Database (/druginteractioninfo.org/), Novartis PK Sciences DDI List (Drug-Drug Interactions (DDI) and Co-medication Considerations for Novartis Clinical Trials, Novartis PK Sciences Internal Memorandum, v01 released in 2018 January).
Food product.	
Herbal product.

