The adaptive Bayesian methodology provides an estimate of all dose levels of VAY736 in combination with 420 mg daily ibrutinib that does not exceed the MTD and incorporates all DLT information at all dose levels for this estimation. In general, the next dose will have the highest chance that the DLT rate will fall in the target interval [16-33%) and will always satisfy the EWOC principle. In all cases, following the half log principle for dose escalation of biologic agents, the dose for the next cohort will not exceed a 3.16 fold increase from the previous dose of VAY736. Smaller increases in dose may be recommended by the Investigators and Sponsor upon consideration of all of the available clinical data.

Any dose escalation decisions made by investigators and Novartis personnel will not exceed the dose level recommended by the BLRM using the EWOC principle. If needed to better define the dose-toxicity relationship additional patients may be enrolled to the current dose level, to a preceding dose level, or to an intermediate dose level before proceeding with further dose escalation.

If 2 patients in a previously untested dose level experience a DLT, enrollment to that cohort will stop, the BLRM will be updated and the next cohort will be opened at the next lower dose level or an intermediate dose level that satisfies the EWOC criteria. However, if 2 patients in a new cohort at a previously tested dose level experience a DLT (e.g., a total of 8 patients are treated on this dose level with 2 DLT observed), further enrollment to that cohort will stop, the BLRM will be updated with this new information and re-evaluation of the available safety, PK, and PD data will occur. By incorporating information gained at the preceding dose cohorts, additional patients may be enrolled into the current dose cohort only if the combination still meets the EWOC criteria and as agreed by Investigators and Novartis personnel. Alternatively, if recruitment to the same cohort may not resume, a new cohort of patients may be recruited to a lower dose combination as agreed by Investigators and Novartis personnel and if the BLRM predicts that the risk for this lower dose combination to exceed the MTD remains below 25% (EWOC). Re-escalation may then occur if data in subsequent cohorts supports this (EWOC criteria are satisfied) and Investigators and Novartis personnel agree.

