10.4.2 Statistical hypothesis, model, and method of analysis

Safety and tolerability

For the analysis of safety and tolerability endpoints see [Section 10.5.3](#) in addition to DLT as below.

Identification of a recommended dose

Estimation of the MTD of the treatment will be based upon the estimation of the probability of DLT in cycle 1 for patients in the DDS. A recommended dose below the MTD may be identified based on other safety, clinical, PK, and PD data ([Section 6.2.3](#)).

Bayesian adaptive approach

The dose escalation part of this study will be guided by a Bayesian analysis of Cycle 1 dose limiting toxicity (DLT) data for VAY736 and ibrutinib. The Bayesian analysis will be based on a model with three parts, representing:

- Single agent VAY736 toxicity
- Single agent ibrutinib toxicity
- Interaction

Single agent toxicity is modelled using logistic regression for the probability of a patient experiencing a DLT against log-dose. The odds of a DLT are then calculated under no interaction for the two single agent toxicities, and interaction is accounted for by adjusting these odds with an additional model parameter (odds multiplier). Details of the model are given in ([Appendix 2](#)).

Assessment of patient risk

After each cohort of patients, the posterior distribution for the risk of DLT for new patients at combination doses of interest will be evaluated. The posterior distributions will be summarized to provide the posterior probability that the risk of DLT lies within the following intervals:

Under-dosing:	[0 , 0.16)
Targeted toxicity:	[0.16 , 0.33)
Excessive toxicity:	[0.33 , 1]

The escalation with overdose control (EWOC) principle

Dosing decisions are guided by the escalation with overdose control principle ([Rogatko 2007](#)). A combination dose may only be used for newly enrolled patients if the risk of excessive toxicity at that combination dose is less than 25%.

Prior distributions

A meta-analytic-predictive (MAP) approach was used to derive the prior distribution for the single-agent VAY736, and single-agent ibrutinib model parameters. The MAP prior for the logistic model parameters for this study is the conditional distribution of the parameters given the historical data (see [Spiegelhalter 2004](#), [Neuenschwander 2010](#), [Neuenschwander 2014](#)). MAP priors are derived from hierarchical models, which take into account possible differences between the studies.

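### Table 14-10 was simulated by giving each cohort the highest dose that passes EWOC, whereas the default in Section 6.2.3 is the admissible dose with the highest target-interval probability, so the quoted 66% and 40% do not describe that default

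*Protocol*

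**What the plan says.** Protocol Section 6.2.3 gives the default for choosing the next dose: "In general, the next dose will have the highest chance that the DLT rate will fall in the target interval" of 16% to 33%, always subject to EWOC. EWOC, in Section 10.4.2, admits a combination for new patients only "if the risk of excessive toxicity at that combination dose is less than 25" percent. Section 6.2.3 also lets the investigators and sponsor take smaller steps after reviewing all the data, and treats the model's recommendation as a ceiling.

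Section 14.2.4.1.1 describes the simulation differently: "the highest VAY736 dose in combination with ibrutinib 420 mg daily satisfying the EWOC criterion is chosen for the next cohort". From it the protocol reports that the probabilities of identifying an MTD in the target region "are approximately 66% for scenario 2 and 40% for scenario 3, respectively", and concludes that the model performs reasonably. SAP Section 3.1.1 leans on the same idea, justifying a minimum of fifteen escalation patients by the model's operating characteristics. Neither document reports a simulation under the Section 6.2.3 default.

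**The concern.** One rule maximises the target-interval probability among admissible doses. The other maximises the dose among admissible doses. They coincide only when the highest admissible dose also has the highest target probability. If they often differ, the operating characteristics offered as evidence for the design belong to a different allocation rule. At stake are the stated chances of a target MTD, of stopping without one, and of treating patients in the target and overdose regions. The point concerns which dose each next cohort receives. It is separate from the conditions for declaring the MTD.

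**Working it through.** **Inputs.** Model from Protocol Section 14.2.1, priors from Table 14-6, true DLT rates from Table 14-9, and simulation settings from Section 14.2.4.1.1 (cohorts of 3-6, at least 15 and at most 40 patients, at least 6 at the MTD, at least 1 DLT).

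**Formulas.** With d1 = 2 × the Q2W dose and ibrutinib at its reference dose of 420 mg:
- logit π1 = log α1 + β1 log(d1/3.0)
- logit π2 = log α2
- π0 = 1 − (1 − π1)(1 − π2)
- odds(π12) = exp(η × d1/3.0) × odds(π0)

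Each prior draw is weighted by the product over doses of π12^r (1 − π12)^(n−r), for r DLTs in n patients. Summing the weights gives P(target) for [0.16, 0.33) and P(excess) for [0.33, 1].

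**Step 1: reproduce the plan's own figures.** From 1.5 million prior draws, P(excess) at 0.1, 0.3, 1.0, 2.0 and 3.0 mg/kg is 0.126, 0.137, 0.176, 0.243 and 0.301. Table 14-7 gives 0.129, 0.139, 0.176, 0.245 and 0.303. The Table 14-8 entries agree to within about 0.01. The model is therefore coded as the protocol intends.

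**Step 2: compare the rules on Table 14-8.** The four non-stopping rows (of ten) where they differ on the provisional grid:

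| Row | Data (DLTs/n) | Highest EWOC dose: P(target), P(excess) | Table 14-8 P(excess) | Dose with highest target probability: P(target), P(excess) |
|---|---|---|---|---|
| 4 | 1/4 at 0.3 | 1.0: 0.313, 0.198 | 0.191 | 0.3: 0.333, 0.135 |
| 7 | 0/3 at 0.3, 1/6 at 1.0 | 3.0: 0.207, 0.233 | 0.233 | 1.0: 0.240, 0.036 |
| 10 | 0/4 at 0.3, 1/6 at 1.0 | 3.0: 0.204, 0.225 | 0.218 | 1.0: 0.221, 0.028 |
| 11 | 1/4 at 0.3, 0/5 at 1.0 | 3.0: 0.172, 0.150 | 0.145 | 1.0: 0.208, 0.028 |

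Table 14-7 also lists an intermediate 2.0 mg/kg. If that dose is open, it has the highest target probability in row 7 (0.248) and row 10 (0.240), and passes EWOC in both (P(excess) 0.133 and 0.123). It still differs from 3.0 mg/kg, so the rules still diverge there. In row 11, 1.0 mg/kg stays ahead (0.208 against 0.200).

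**Step 3: simulate both rules.** Settings: 4,000 trials per cell, start at 0.3 mg/kg, four-dose grid, cohort sizes 3-6 equally likely. Escalation is at most one provisional level at a time, as Table 14-8 does. (The step from 0.3 to 1.0 is 3.33-fold, slightly above the 3.16-fold limit in Section 6.2.3.) The Monte Carlo standard error of each percentage is at most √(0.25/4000) = 0.8 points. The way the MTD is picked is not documented, so three versions were tried. Chance of a target MTD, highest-EWOC rule → Section 6.2.3 default:

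| MTD pick | Scenario 2 | Scenario 3 |
|---|---|---|
| Highest target probability, admissible, n ≥ 6 | 68.8 → 57.4 (−11.4) | 41.0 → 52.5 (+11.5) |
| Highest admissible dose, n ≥ 6 | 72.2 → 59.5 (−12.7) | 40.6 → 52.5 (+11.9) |
| Next recommended dose | 78.6 → 63.4 (−15.2) | 40.8 → 51.6 (+10.8) |
| Table 14-10 | 66.3 | 39.9 |

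The first version comes closest to Table 14-10: 68.8 − 66.3 = 2.5 points off in Scenario 2 and 41.0 − 39.9 = 1.1 in Scenario 3. In that version the default also moves:
- Scenario 2, patients in the target region: 57.9% to 47.2%
- Scenario 2, under-dose MTD: 16.9% to 28.0%
- Scenario 3, patients overdosed: 36.6% to 29.9%
- Scenario 3, stopped without an MTD: 47.8% to 36.2%
- Scenario 3, overdose MTD: 8.9% to 9.6%, little changed

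Varying cohort size (fixed 3 to 6, or mixed) and the declaration rule as well, Scenario 2 falls by about 10 to 19 points and Scenario 3 rises by about 1.5 to 24. A separate run with cohorts of 3-6 gave about 80% against 58% in Scenario 2, which extends that range to 22.

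**Step 4: which rule does the published table fit?** Scenario 2 patients in the target region are printed as 62.2%; the set-ups gave 54-66% under the highest-EWOC rule and 40-55% under the default. Scenario 3 stopping is printed as 52.2%; the set-ups gave 37-59% and 31-41%. Both printed values lie within the first range and outside the second.

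**The case against.** The strongest reply is that Section 6.2.3 is not a fixed algorithm. It speaks in general terms, permits smaller steps, and (with Section 8.5) rests on a synthesis of all data, so no simulation can represent it fully. The simulated rule is openly stated, and Section 14.2.3 labels the Table 14-8 doses as maxima. Section 6.2.3 also describes the MTD as typically the highest tested combination that passes EWOC. All of this is fair, and it limits what can be claimed about real decisions. It does not make the highest admissible dose the default for assigning cohorts, and the stated default is what a simulation should represent.

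A reader might infer more than the documents support:
- *That the protocol wrongly asserts the simulation obeys Section 6.2.3.* The words "and follows the protocol specifications (Section 6.2.3" have the starting dose combination as their grammatical subject and may refer to that alone. The mismatch stands without them.
- *That Table 14-10 is miscalculated.* The failure to reproduce it exactly reflects undocumented settings and does not show an error.
- *That overdose control is overstated.* In Scenario 3 the default treats fewer patients in the overdose region and stops less often, and the chance of an excessively toxic MTD barely moves.
- *That patients received wrong doses.* Escalation finished with 15 patients. The Amendment 03 rationale reports no DLTs in the first eleven. In the zero-DLT rows of Table 14-8 (1 and 5) the two rules agree on the provisional grid.

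**Conclusion.** The point holds as a mismatch between the stated default and the simulated rule. The Table 14-10 figures, including the 66% and 40%, are properties of the highest-EWOC rule. Under the Section 6.2.3 default the chance of a target MTD is lower in Scenario 2 by roughly 10 to 22 points and higher in Scenario 3 by roughly 1.5 to 24 points. The directions were the same in every paired set-up. The sizes are not firm: they rest on the four-dose grid, on assumed cohort-size distributions and MTD picks, and on applying the default without clinical override. The divergence in rows 4, 7, 10 and 11 depends on the documented model and dose grid, and on none of the simulation settings.

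The practical stakes are moderate. Escalation is complete, the SAP records early termination for business reasons, and the MTD estimate comes from the trial's own posterior. What remains affected is the documented justification of the design.

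**What to change.** Reconcile Protocol Section 6.2.3 with Section 14.2.4.1.1 on how each cohort's dose is assigned. Which rule is right is for the sponsor and investigators, and this review takes no position. Then do one of the following:
- Re-run Table 14-10 under the stated default, or show both rules side by side. State the dose grid (including whether 2.0 mg/kg is open), the cohort-size distribution and how the MTD is picked.
- Keep the existing figures and label them as applying to the highest-EWOC rule only.

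In either case, revise the percentages and the statement of reasonable performance to match. The cost is one re-run of existing simulation code and an edit to Appendix 2, or the edit alone. After a re-run, Scenario 2 would look less favourable and Scenario 3 more so.
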